### Statistical Pre-analysis:

The sample size was calculated using the online calculator at [www.sealedenvelope.com](http://www.sealedenvelope.com). Assuming a power of 90% and an error margin of 5%, the required number for each group (experimental and control teeth) was found to be 43. Since a split-mouth design will be used, in which each patient will have both experimental and control groups, the required number of participants was also determined to be at least 43. Considering possible dropouts during the study, the final sample size was set at 50 participants. Randomization will be achieved using a blocked randomization technique at [www.sealedenvelope.com](http://www.sealedenvelope.com). For blocked randomization, the seed number will be set as 12345 and block size as 2.

In the second phase, volunteer participants will be selected among patients who apply to the Faculty of Dentistry, Başkent University, and are referred to the Department of Restorative Dentistry for treatment after clinical and radiological examination revealed carious lesions. The inclusion criteria will be as follows:

- Voluntary acceptance of participation in the study
- Age between 18–65 years
- Presence of at least 12 teeth in occlusion
- The teeth to be included must have natural antagonists and adjacent teeth (normal occlusion)
- Anterior or posterior teeth with primary or secondary carious lesions in which the cavity preparation is expected to approach the pulp closely but without pulpal exposure
- Each participant must have two teeth, one on the right and one on the left, fulfilling the above criteria
- Absence of any other factor causing sensitivity or pain that might interfere with evaluation

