When necessary depending on cavity type, a matrix system (Mylar strip, sectional matrix, or Tofflemire) will be applied before restoration. All cavities will be treated with a one-step self-etch adhesive (Clearfil SE Bond, Kuraray Noritake, Tokyo, Japan) according to manufacturer's instructions and light-cured with an LED unit (LedMax Cordless 550, Benlioğlu Dental, Ankara, Turkey) at a constant intensity  $>1,500$  mW/cm^2 for 10 seconds. Restorations will be completed using a universal composite resin (Filtek Z250, 3M Espe, St. Paul, MN, USA) with the oblique incremental technique. Each increment of composite will be polymerized for 20 seconds with the same LED device. Finishing and polishing will be performed using diamond finishing burs, polishing rubbers, and disks (Soflex, 3M Espe, St. Paul, MN, USA). All restorations will be performed by a single operator.

After restoration, participants will be given two forms (one for each tooth) to record their daily pain levels for one week. Instructions for filling out the forms will be provided. The forms will include the Numerical Rating Scale (NRS, 0–4) and the Visual Analog Scale (VAS, 0–100 mm). One week later, patients will return for follow-up, and the completed forms will be collected. Six weeks after the restorations, patients will return for another follow-up. At both the one-week and six-week follow-up visits, restorations will be evaluated by another dentist to ensure double blinding.

At the one-month control visit, tooth vitality will first be assessed. If the tooth is vital, postoperative sensitivity will be evaluated using VAS scores and by applying a cold spray (Ice Spray, Picdare S.p.A, Casnate con Bernate, Italy) with a cotton pellet to the mid-buccal surface of the teeth for 5 seconds.

Study Start Date: May 3, 2021

Study Completion Date: May 3, 2022

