## STATISTICAL ANALYSIS

Measurements will be obtained from two paired teeth of the same patient. The VAS and NRS values of these paired groups will be compared. For this purpose, chi-square test will be used for NRS values, and independent two-sample t-test will be used for VAS values. The significance level will be set at  $p = 0.05$ .

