## EXPECTED OUTCOMES AND SCIENTIFIC CONTRIBUTIONS

The aim of this study is to evaluate the effect of applying a hydroxyapatite-forming desensitizing material (Teethmate Desensitizer) to the cavity prior to restoration, compared with a control. Teethmate Desensitizer is a biocompatible material. Therefore, it may be effective in reducing postoperative sensitivity in cavities and increasing patient comfort.

As a result of this original study, it is expected that data on the effect of using Teethmate Desensitizer beneath restorative materials on postoperative sensitivity will contribute both to national and international literature.

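### The 0–4 NRS comes from paired teeth, but the planned chi-square test ignores both the pairing and the order of the scores and can lose a large share of the power

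*Combined protocol and SAP*

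**What the plan says.** The Statistical Pre-analysis section sets out the design: "Since a split-mouth design will be used, in which each patient will have both experimental and control groups". The Statistical Analysis section repeats the structure: "Measurements will be obtained from two paired teeth of the same patient". It then gives the rule for this outcome: "chi-square test will be used for NRS values".

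The scale and its recording are described in the third phase of Materials and Methods (the text that follows the exclusion criteria). The scale has five levels: "The forms will include the Numerical Rating Scale (NRS, 0–4". It is filled in every day: "participants will be given two forms (one for each tooth) to record their daily pain levels for one week". The expected effect has a direction, since the Expected Outcomes section says of the agent that "it may be effective in reducing postoperative sensitivity in cavities and increasing patient comfort".

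The documents name no paired categorical test, rank test, trend test or ordinal model. They do not describe reducing the NRS to yes/no, and they do not say which day or weekly summary is to be tested.

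**The concern.** The usual chi-square test on a table of NRS level by treatment rests on two premises. One is that all observations are independent, which the plan itself contradicts by calling the teeth paired. The other is that the categories have no order, which a 0–4 pain score contradicts. With five levels the test has 4 degrees of freedom and spreads its sensitivity over every kind of difference in distribution, when the trial wants to detect a shift towards lower scores.

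The NRS is one of only two measures named in the analysis section, and neither is ranked above the other. The stake is that a real reduction in pain is missed. In the other direction, a significant chi-square could reflect a change in spread with no change in average pain.

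This point concerns the NRS only, not the t-test planned for the VAS.

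**Working it through.** **The plan's own figure.** The sample size section gives 90% power, a 5% error margin and 43 teeth per group, and carries this over to patients: "the required number of participants was also determined to be at least 43". It is raised to 50 for dropout. No effect size, SD, event rate or correlation is given, so 43 cannot be reproduced, only back-solved. For two independent means, n = 2(1.960 + 1.282)²/δ², and n = 43 gives δ = √(2 × 10.51/43) ≈ 0.70 SD. I therefore used latent shifts of 0.5 and 0.7 SD. The plan does not say that 43 was based on the NRS.

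**Example 1: a consistent benefit that chi-square misses.** Of 43 patients, 14 score one point lower on the desensitizer tooth, 3 score one point higher and 26 score the same. One set of counts at levels 0–4 that fits is 15/11/9/5/3 (control) and 19/10/9/3/2 (desensitizer).

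- With equal group totals, chi-square = Σ(a − b)²/(a + b) = 16/34 + 1/21 + 0/18 + 4/8 + 1/5 = 1.22 on 4 df, p = 0.875.
- All 17 non-zero differences have size one, so the exact signed-rank test reduces to a binomial: p = 2 × (1 + 17 + 136 + 680)/2¹⁷ = 1668/131072 = 0.0127.

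**Example 2: significance without less pain.** Counts 4/10/15/10/4 and 12/6/7/6/12 both sum to 86 points over 43 teeth, a mean of 2.0. Chi-square = 64/16 + 16/16 + 64/22 + 16/16 + 64/16 = 12.91 on 4 df, p = 0.0117.

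**Power.** Assumptions: one score per tooth; bivariate-normal latent scores with within-patient correlation ρ; control distributions 60/20/10/6/4%, 35/25/20/12/8% and 20% at each level; two-sided 5% (the plan does not state sidedness). Pearson chi-square (empty levels dropped) was compared with the normal-approximation signed-rank test (zero differences dropped) in 5,000 simulated trials per scenario. The simulation standard error is at most √(0.25/5000) = 0.7 points. Ranges run over the three distributions, with 43 pairs.

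| ρ | Shift 0.5 SD: chi-square | Shift 0.5 SD: signed-rank | Shift 0.7 SD: chi-square | Shift 0.7 SD: signed-rank | No effect: chi-square rejects |
|---|---|---|---|---|---|
| 0 | 23–35% | 42–56% | 43–65% | 67–83% | 3.8–5.3% |
| 0.3 | 20–35% | 50–68% | 41–68% | 76–93% | 3.2–3.7% |
| 0.5 | 19–30% | 61–80% | 40–67% | 84–97% | 2.2–2.7% |
| 0.7 | 15–28% | 76–94% | 38–67% | 95–100% | 1.4–1.6% |

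The signed-rank test rejected in 4.2–5.6% of trials with no effect. The ratio of chi-square to signed-rank power at shift 0.5 is 0.54–0.63 at ρ = 0 and 0.31–0.38 at ρ = 0.5. The relative loss is therefore 37–46% and 62–69%. At shift 0.7 the ratios are 0.63–0.78 and 0.48–0.69, a loss of 22–37% and 31–52%.

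With all 50 pairs and ρ = 0.5, power is 22–38% against 67–86% (shift 0.5) and 50–77% against 90–99% (shift 0.7).

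**Order and pairing separated.** A rank-sum test uses order but ignores pairing, so it splits the loss. These figures come from 3,000 simulated trials per scenario, with control distribution 40/25/20/10/5%, 43 pairs and ρ = 0.5.

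| Shift | Chi-square | Rank-sum | Signed-rank | Lost by ignoring order | Further lost by ignoring pairing |
|---|---|---|---|---|---|
| 0.5 SD | 25.0% | 53.7% | 73.7% | 28.7 points | 20.0 points |
| 0.7 SD | 55.9% | 84.7% | 93.3% | 28.8 points | 8.6 points |

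At ρ = 0 the pairing loss vanishes. The order loss remains: at shift 0.7, chi-square against rank-sum is 58% against 80% for this distribution.

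**The case against.** The strongest objection is that every power figure rests on assumptions, because the documents supply no NRS distribution, effect size or correlation. That is true. A scale with mostly zeros is also plausible. With 80/12/5/2/1% and ρ = 0.5, power is about 9% against 36% at shift 0.5 and 20% against 58% at shift 0.7. With 90% zeros it is about 4% against 18% and 7% against 28%. The signed-rank test still does better, but it would not give adequate power there, so the table does not predict what the trial would gain.

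Second, the test is conservative only if each tooth contributes one score, which the plan does not say. If all tooth-days were pooled into one table, the false-positive rate would rise. It was about 7–20% with 43 pairs, control distribution 35/25/20/12/8%, and assumed variance shares of 0.3–0.6 for patient and 0.1–0.3 for tooth within patient. This limits the statement about direction of harm but does not help the plan.

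Third, the NRS is not named as primary and 43 is not tied to it, so the loss cannot be set against a promised NRS power. That stands. With no stated hierarchy, though, the NRS cannot be set aside as secondary either.

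Finally, the choice of summary and of paired method is partly preference. The signed-rank test ranks sizes of differences and so treats a step from 0 to 1 like a step from 3 to 4. The need for a paired method that respects order is not a matter of preference.

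**Conclusion.** The point holds. The plan assigns a test for independent, unordered categories to data that it describes as paired and defines as ordered, and nothing elsewhere in the documents corrects this. It is a stated rule that does not fit the design, not a missing detail.

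Under the assumptions shown, with 43 pairs and a 0.5 SD shift, chi-square loses about half or more of the available power once the within-patient correlation reaches 0.3, and more than a third even at zero correlation. At a 0.7 SD shift the loss is smaller but still 22% or more. The direction was the same in every scenario with a true effect; the exact size cannot be fixed from the documents. With one score per tooth and positive correlation, the harm is a missed effect, not a false claim. The missing day or summary is a linked gap that would remain under any test.

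**What to change.** In the Statistical Analysis section, replace the chi-square rule with a paired analysis that uses the order of the scores, and name the NRS summary. Possible wording: *For each tooth the NRS outcome is the worst score over the seven diary days. The two teeth of each patient will be compared by a two-sided Wilcoxon signed-rank test on the within-patient difference, with zero differences dropped.* The seven-day mean could be named instead. To use all daily scores, specify a cumulative-logit mixed model with random effects for patient and for tooth within patient. For any yes/no summary, such as any sensitivity, use McNemar's test.

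The cost is two or three sentences. The forms already planned supply the data, and no patients are added. The summary should be fixed before the data are examined. Because the protocol gives a completion date of May 3, 2022, the change should be dated and documented. If the scores have already been seen, the report should say so.

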## EXPECTED OUTCOMES AND SCIENTIFIC CONTRIBUTIONS

The aim of this study is to evaluate the effect of applying a hydroxyapatite-forming desensitizing material (Teethmate Desensitizer) to the cavity prior to restoration, compared with a control. Teethmate Desensitizer is a biocompatible material. Therefore, it may be effective in reducing postoperative sensitivity in cavities and increasing patient comfort.

As a result of this original study, it is expected that data on the effect of using Teethmate Desensitizer beneath restorative materials on postoperative sensitivity will contribute both to national and international literature.

